### 14.3. Statistical analysis

Statistical analyses will be detailed in the statistical analysis plan developed before the database is frozen.

Baseline characteristics, compliance to treatment, safety, and carcinologic events will be described.

Qualitative data will be described by frequencies and percentages and associated 95% confidence interval.

Continuous parameters will be described by mean, standard deviation, median and range.

The primary endpoint will be described by the percentage of patients without fibrosis at 12 months and its 95% confidence interval.

For secondary endpoints, EORTC QLQ-C30 and QLQ-BR23 will be described according to EORTC scoring manual at baseline and for each visit.

Time to event endpoints (L-RFS, M-RFS, DFS, OS and mastectomy-free interval) will be estimated using Kaplan-Meier method and described by their rates and 95% confidence intervals at 12 months, 24 months, and 3 years.

Statistical analyses will be performed with STATA software v13 (Stata Corporation, College Station, TX, USA).

#### **14.4. Study population**

\*Intention to treat population (ITT) = all included patients analyzed, non-evaluable patients will be considered as failure.

\*Per-Protocol population (PP) = all eligible (patients presenting a major deviation from the inclusion/exclusion criteria will not be selected) and evaluable patients.

\*Evaluable population: all patients included, with postoperative histological results that meet the inclusion criteria and at least 3 assessments before 12 months.

\*Safety population: all patients included in the ITT population, operated and treated with Intraoperative Radiotherapy.

All statistical analyses will be performed on ITT population, on evaluable population and PP population for primary endpoint and on Safety population for safety.

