Assessment criteria	
Primary criterion:
 
 
- grade <math>\geq</math> 2 late fibrosis, according to the NCI CTCAE v4.0 grading scale, occurring within 12 months following the IORT.
 
 
Secondary criteria:
 
Definitive cosmetic results:
 
 
- assessed by a physician and the patient
 
- Pictures will be taken before treatment, after 15 days, three, six, and twelve months then 1fs / year up to five years.
 
 
Toxicities Evaluation :
 
 
- assessed by a physician
 
 
Quality of life:
 
 
- assessed by a patient
 
- EORTC QLQ-C30, QLQ-BR23 questionnaires delivered before treatment, and after 15 days, three, six, twelve months and twenty-four months.
 
 
Local relapse-free survival (L-RFS):
 
 
- L-RFS is defined as the time from surgery with IORT to any ipsilateral breast tumor recurrence, or death, whichever occurs first.
 
 
Metastasis Relapse-free survival (M-RFS):
 
 
- M-RFS is defined as the time from the surgery with IORT to any metastatic disease (excluding the ipsilateral breast, contralateral breast, regional lymph nodes), or death, whichever occurs first.
 
 
Disease-free survival (DFS):
 
 
- DFS is defined as the time from the surgery with IORT to any recurrence, including local recurrence, metastasis, appearance of a
 

	
second primary tumor, or death from any cause, whichever occurs first.
 
Overall survival (OS):
 
 
- OS is defined as the time from surgery with IORT to death from any cause.
 
 
Mastectomy-free interval:
 
 
- MFI is defined as the time from the surgery with IORT to a mastectomy for any reasons (all other events will be ignored). All patients without mastectomy will be censored at last follow-up.
 

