STATISTICAL CONSIDERATIONS	
Sample size calculation
 
The primary endpoint is the success rate at 12 months, the success being defined as no grade <math>\geq 2</math> fibrosis according to NCI-CTCAE V4.0 classification.
 
A success rate of 95% is expected. The sample size calculation is based on:
 
 
• The Fleming one-stage design with one-sided alpha=0.05 and beta=0.05.
 
• <math>p_0 = 80\%</math> (success rate at 12 months, threshold below which we will consider the Intraoperative Radiotherapy toxicity as unacceptable, assuming 20% failure)
 
• <math>p_1 = 95\%</math> (success rate target at 12 months)
 
 
A total of 46 evaluable patients is required; taking into account un-evaluable patients, the number of subjects is adjusted to 65
 
It should be noted that the alpha level is set at 5% (one-sided), risk of concluding as to efficacy (<math>p > p_0</math>) whereas there is no efficacy (<math>p \leq p_0</math>), and the beta level is set at 5%, risk of concluding as to the absence of efficacy (<math>p < p_1</math>) whereas there is noteworthy efficacy (<math>p \geq p_1</math>)
 
After inclusion of 46 evaluable patients (at least 3 assessments within 12 months), it will be possible to conclude that the study demonstrates inefficacy if the success number is less than or equal to 40, or efficacy if the success number is greater than or equal to 41.
 
The patient size and the decision rule are presented here-below:
 
  
 Hyp	Rate of success at 12 months	<math>p_0</math>	<math>p_1</math>	Fleming one stage design*	N total	
   
 Rate		80	95	(46, <math>\leq 40</math>, <math>\geq 41</math>)	65	
  
 
*(N, n1, n2)
	Hyp	Rate of success at 12 months	$p_0$	$p_1$	Fleming one stage design*	N total	Rate		80	95	(46, $\leq 40$ , $\geq 41$ )	65
Hyp	Rate of success at 12 months	$p_0$	$p_1$	Fleming one stage design*	N total								
Rate		80	95	(46, $\leq 40$ , $\geq 41$ )	65								

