## 9-Primary endpoint

The fibrosis grade will be scored following the NCI CTCAE scale v4.0 at 12 months after the IORT (73).

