### 14.1. Sample size calculation

The primary objective is to evaluate the success rate at 12 months, defined as the non-observation of fibrosis at 12 months after IORT.

A success rate of 95% is expected. The sample size calculation is based on:

- The Fleming one-stage design with one-sided alpha=0.05 and beta=0.05.

- $p_0 = 80\%$  (success rate at 12 months, threshold below which we will consider the Intraoperative Radiotherapy toxicity as unacceptable, assuming 20% failure)
- $p_1 = 95\%$  (success rate target at 12 months)

A total of 46 evaluable patients are required; taking into account non-evaluable patients (postoperative histological results that do not meet the inclusion criteria or less than 3 assessments before 12 months), the number of subjects is adjusted to 65.

It should be noted that the alpha level is set at 5% (one-sided), risk of concluding as to efficacy ( $p > p_0$ ) whereas there is no efficacy ( $p \leq p_0$ ), and the beta level is set at 5%, risk of concluding as to the absence of efficacy ( $p < p_1$ ) whereas there is noteworthy efficacy ( $p \geq p_1$ ).

After inclusion of 46 evaluable patients, it will be possible to conclude that the study arm demonstrates inefficacy if the success number is less than or equal to 40, or efficacy if the success number is greater than or equal to 41.

The sample size and the decision rule are presented here-below:

Hyp.	Rate of success at 12 months	$p_0$	$p_1$	Fleming one-stage design *	N total
Rate		80	95	(46, $\leq 40$ , $\geq 41$ )	65

\* (N,  $n_1$ ,  $n_2$ )

N = total sample size required.

$n_1$  = maximal number of success required to conclude => non-efficacy.

$n_2$  = minimal number of success required to conclude => efficacy.

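### Evaluability for the primary endpoint counts three assessments before 12 months but does not require the 12-month fibrosis grade on which success is scored

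*Protocol*

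**What the plan says.** **Who is evaluable.** Section 14.4 defines the evaluable population as "all patients included, with postoperative histological results that meet the inclusion criteria and at least 3 assessments before 12 months". Section 14.1 gives the same rule in the negative; patients are non-evaluable for "postoperative histological results that do not meet the inclusion criteria or less than 3 assessments before 12 months". The Statistical considerations part of the synopsis uses a different preposition: "After inclusion of 46 evaluable patients (at least 3 assessments within 12 months".

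**When the endpoint is scored.** Section 9: "The fibrosis grade will be scored following the NCI CTCAE scale v4.0 at 12 months after the IORT". Section 14.1 describes success as "defined as the non-observation of fibrosis at 12 months after IORT", and section 14.3 states: "The primary endpoint will be described by the percentage of patients without fibrosis at 12 months". The Assessment criteria part of the synopsis is worded differently. It counts late fibrosis of grade 2 or more "occurring within 12 months following the IORT".

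**What happens to the others.** Section 14.4 defines ITT as "all included patients analyzed, non-evaluable patients will be considered as failure". The per-protocol set is drawn from eligible and evaluable patients, so it inherits the same definition. The primary endpoint is to be analysed on all three sets, and the decision rule (41 or more successes) is applied to 46 evaluable patients.

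**Schedule.** Section 11 has radiation-induced toxicity recorded at 15 days, 3, 6 and 12 months and later, and lists fibrosis among the delayed toxicities, beyond 6 months.

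**The concern.** An evaluability rule should pick out the patients in whom the endpoint was observed. This one counts earlier visits instead, and it can go wrong in two directions.

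First, a patient seen at day 15, month 3 and month 6 and then lost has met the count. All three visits precede the window in which the protocol itself lists fibrosis. She enters the 46 with no 12-month outcome, and because she is evaluable, the ITT failure rule leaves her alone.

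Second, a patient who attends at month 12 and is graded may be classed as non-evaluable, and hence as an ITT failure whatever her grade, because she missed one early visit. This follows only if the wording of section 14.4 excludes the month-12 visit and baseline is not an assessment. Under the synopsis wording the same patient is evaluable.

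The rule allows only 46 − 41 = 5 failures, so a handful of misplaced patients can change the result.

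**Working it through.** **1. Inputs.** p0 = 80%, p1 = 95%, one-sided alpha 0.05, beta 0.05, N = 46 evaluable, positive if 41 or more successes (section 14.1). Visits before month 12: day 15, month 3, month 6 (section 11). The number m of evaluable patients without a 12-month grade is not in the protocol; I take m = 1, 2 or 3 as an assumption.

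**2. The protocol's own figure.** Normal approximation: n = [(1.645·√(0.80·0.20) + 1.645·√(0.95·0.05)) / (0.95 − 0.80)]² = 45.9, rounded up to 46. The stated sample size reproduces. The exact binomial for the stated rule gives P(X ≥ 41 | 46, 0.80) = 0.0798 and P(X ≥ 41 | 46, 0.95) = 0.9737. The excess of 0.0798 over 0.05 comes from the cut-off and is a separate matter; it serves here only as the baseline.

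**3. Three patients, classified under each wording** (baseline not counted)

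| Patient | Sections 14.1 and 14.4, month 12 not counted | Synopsis, month 12 may count | 12-month grade known? |
|---|---|---|---|
| Seen at day 15, months 3 and 6, then lost | Evaluable | Evaluable | No |
| Seen at day 15, months 6 and 12 | Non-evaluable, ITT failure | Evaluable | Yes |
| Seen at all four visits | Evaluable | Evaluable | Yes |

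The first row is wrong under either wording. The second depends on the wording.

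**4. Effect on the decision rule.** With m of the 46 ungraded:

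- scored as successes: P(Bin(46 − m, p) ≥ 41 − m)
- scored as failures: P(Bin(46 − m, p) ≥ 41)

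| m | Positive at 80%, scored success | Positive at 80%, scored failure | Power at 95%, scored success | Power at 95%, scored failure |
|---|---|---|---|---|
| 0 | 0.0798 | 0.0798 | 0.9737 | 0.9737 |
| 1 | 0.0902 | 0.0382 | 0.9761 | 0.9271 |
| 2 | 0.1018 | 0.0151 | 0.9784 | 0.8235 |
| 3 | 0.1145 | 0.0046 | 0.9806 | 0.6352 |

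The success column treats every ungraded patient as a certain success, so it is the upper end of that effect. Some of these patients would already have shown fibrosis by month 6 if the endpoint is read as cumulative.

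**The case against.** **The analysis plan may deal with it.** Section 14.3 defers detail to a statistical analysis plan, and the scoring of a missing 12-month grade can properly sit there. That stands, so the absence of a scoring rule is not the charge. But the protocol itself fixes the evaluable set, the ITT failure rule that hangs on it, and the count to which the cut-off applies. That fixed definition does not match the time at which the endpoint is scored.

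**The synopsis endpoint is cumulative.** If fibrosis at any time up to 12 months counts, a minimum number of looks is an intelligible rule, and an early qualifying grade settles a failure without the last visit. This is fair, but success still cannot be established without observation to month 12.

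**The second direction is fragile.** The protocol does not define an assessment, and the flowchart also schedules clinical and breast skin evaluation at baseline. If baseline counts, a patient graded at month 12 is lost only after missing two early visits. A reader might infer that the literal wording would discard several of the 65 patients. The protocol does not support that: it gives no rate of missed visits, and the result turns on what counts as an assessment. Counting baseline makes the first direction worse, because baseline, day 15 and month 3 would then suffice.

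**The false-positive risk need not rise.** A reader might infer that the gap favours a positive result. No scoring is stated, so the direction is open. Scoring ungraded patients as failures lowers the false-positive risk, which is the cautious side in a toxicity trial, at a cost in power.

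**Conclusion.** The concern holds in this form: the evaluability rule in sections 14.1 and 14.4 admits patients whose 12-month outcome was never observed, and the ITT failure rule does not catch them. This follows from the text alone and does not depend on any assumed rate. The difference in preposition between the synopsis and section 14 is a further inconsistency to reconcile. It reclassifies patients only if month 12 and baseline are both excluded from the count.

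The size is illustrative, since it rests on an assumed 1 to 3 ungraded patients among 46 and on how they are scored. Scored as successes, they add 1.0, 2.2 or 3.5 percentage points to the 8.0% chance of a positive result at a true 80%. Scored as failures, they cut that chance to 3.8%, 1.5% or 0.5% and cost about 5, 15 or 34 points of the 97.4% power.

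A reader might also infer that grade 2 or worse fibrosis at any visit must count as a failure. The protocol does not settle this. The synopsis speaks of late fibrosis within 12 months, while sections 9, 14.1 and 14.3 look at status at 12 months.

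This should be corrected before the analysis. It does not undermine the design.

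**What to change.** 1. In the synopsis (Statistical considerations) and sections 14.1 and 14.4, replace the three-assessment count with the requirement of a fibrosis grade at the 12-month visit. An ungraded patient then becomes non-evaluable and falls under the existing ITT failure rule. A patient graded at month 12 is no longer lost for a missed early visit.
2. The sponsor should state one endpoint throughout: either status at 12 months (sections 9, 14.1, 14.3) or late fibrosis of grade 2 or more occurring within 12 months (synopsis, Assessment criteria). If the second is chosen, a qualifying earlier failure also makes the patient evaluable.
3. State the cut-off, with its exact alpha and power, for the number of patients actually analysed. For example, with 50 evaluable patients and 45 or more successes, alpha is 0.048 and power 0.962.

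**Cost.** Wording only; the 12-month visit is already scheduled. The number evaluable may change, which is why item 3 is needed. Under the cumulative endpoint, early failures stay in the evaluable set while other ungraded patients leave it, so that analysis leans slightly against success.

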#### **14.5. Modifications of the statistical analysis plan and initial strategy**

Any modification to the initial statistical analysis plan (PAS) will be detailed with all the necessary arguments reported in an updated version of PAS. These modifications can include supplementary or exploratory analyses that were not initially planned.

### **15- Proteomics and IORT late-side effects (Mandatory)**

#### **15.1. Sample collection:**

21 ml EDTA whole blood will be collected before starting radiotherapy.

#### **15.2. Lymphocytes separation:**

Immediately, lymphocytes will be isolated with ficoll density gradient centrifugation (Ficoll-Paque PLUS, GE Healthcare) following manufactory recommendations. This protocol will allow recovering 7.5 to 15 million cells per patient. Purified lymphocytes will be cultured in two dishes containing RPMI 1640 medium (Gibco BRL Invitrogen) supplemented with 20% FCS during 24h. For each patient, one cell culture dish will be irradiated at 8 Gy and incubated for 48 hours, and one cell culture will be shammed irradiated and considered as control (0 Gy).

### 15.3. Western blot analyses:

Lymphocytes proteins will be extracted by RIPA buffer. Cell lysates will be quantitated using the BCA protein assay kit (ThermoFisherScientific, Rockford, IL) according to the manufacturer's protocol. Ten micrograms of proteins will be then loaded and separated on 12% SDS-PAGE and then transferred to a PVDF membrane. Nonspecific binding to the membrane is blocked for 1 hour at room temperature with 5% nonfat milk. Membranes will be incubated overnight at 4°C with the primary antibodies diluted as follows: AK2 (1/200, sc-28786; Santa Cruz Biotechnology, Inc., Santa Cruz CA), Annexin-1 (1/200, sc-11387; Santa Cruz Biotechnology, Inc., Santa Cruz CA), HSC70 (1/500, sc-7298; Santa Cruz Biotechnology, Inc., Santa Cruz CA), IDH2 (1/100, sc-134923; Santa Cruz Biotechnology, Inc., Santa Cruz CA) and Ref-1 (1/300, sc-5572; Santa Cruz Biotechnology, Inc., Santa Cruz CA). Membranes will be then incubated with secondary antibody (goat anti-rabbit IgG (H+L), G21234; Invitrogen for AK2, Annexin-1, IDH2, Ref-1 and goat anti-mouse IgG (H+L), 115-035-146; Jackson ImmunoResearch for HSC70) for 1 hour at room temperature. The immunoblots will be developed using the enhanced chemiluminescence detection system with the use of a SuperSignal West Pico Chemiluminescent Substrate kit (Pierce). Image analyses will be performed using ImageJ software (National Institutes of Health, Bethesda, MD).

### 15.4. Development of an ELISA assay for the five candidate proteins:

In order to propose a reliable, rapid and easy to used assay, an ELISA strategy will be developed. Two antibodies will be produced for each protein by Abnova against antigenic peptides (5 months). The company provides the antibodies already tested for ELISA. A sandwich-ELISA test will be established in a 96-well format, using the antigen used for antibody production. The latter will also serve as quantification standard. For each protein, one antibody serves to capture the target and will be used to coat the wells. The other antibody will be linked to biotin with the EZ-Link Sulfo-NHS-Biotinylation Kit from Pierce. Streptavidin-HRP together with an appropriate substrate buffer will be used for detection. The whole procedure should be achieved within one year. Concentration of the five candidate proteins will be measured in the cell extracts obtained above with this test.

## 16- GENOMIC and IORT (Optional)

---

The miRNA expression profiles are altered in a specific and radiation dose-dependent manner (an mRNA radiation exposure "signature") that provides a sensitive and effective, biodosimetry test.

## 16.1. Serum collection from resected cavity (Investigation centers, France):

In all investigation centers involved in the genomic assay, 5 ml of operative cavity serum will be collected from each patient before IORT and 5 ml after the IORT (one single dose of 21 Gy IORT). Five volumes of RNAProtect Cell Reagent (Qiagen) will be mixed with one volume of serum and immediately stored at -80C until shipping to the ICM. Samples will be regrouped at the ICM and send to the University of Arizona.

## 16.2. miRNA isolation (Phoenix, AZ, US):

After shipping the samples will be stored at -80°C until processing where miRNA will be isolated from the cells using the TaqMan miRNA ABC purification kit (Life Technologies) according to the manufacturer's instruction.

## 16.3. qRT-PCR and analysis (Phoenix, AZ, US):

Purified miRNA will be converted to cDNA and analyzed by quantitative PCR using the TaqMan array human MicroRNA (LifeTechnologies) according to the manufacturer's instruction to screen the miRNA for profile changes in response to irradiation.

## 16.4. CLPA analysis (Phoenix, AZ, US):

Once the miRNA signature will be optimized with the qRT-PCR, we will implement the CLPA assay using a customized panel with the selected miRNA from the qRT-PCR to follow the changes in expression to validate the assay chemistry. Future integration into a microfluidic platform will be explored for implementation in a rapid biodosimetry point of care system.

# 17- Study monitoring and data collection

---

## 17.2. Study monitoring

A Clinical Research Associate (CRA) will be appointed by the Sponsor to monitor this study.

CRA activities include: Site initiation visit to collect and distribute essential pre-study documents; to instruct the investigator and site personnel about the protocol, study procedures and expectations; to obtain investigator's assurance to comply with study requirements and GCP guidelines and to inform the investigator and appropriate study staff about study materials.

Monitoring visits : according to the Good Clinical Practice Guidelines, the study CRAs involved in the present study are fully instructed concerning confidentiality and able to perform any necessary control on informed consent and CRFs, including cross-checking clinical and laboratory data with the patient's file. All observations and findings should be verifiable. During monitoring visits, the Sponsor CRAs will:

- check and assess the progress of the study;
- review study data collected;
- conduct Source Document Verification (hospital files);
- identify any issues and address its resolution;

This will be done in order to verify that the:

- Data are authentic, accurate, and complete.
- Safety and rights of subjects are being protected;
- Study is conducted in accordance with the currently approved protocol (and any amendments), GCP and all applicable regulatory requirements.

The investigator agrees to allow the CRA direct access to all relevant documents and to allocate his/her time and the time of his/her staff to the CRA to discuss findings and any relevant issues.

## 17.3. Case Report Form (CRF)

Study data will be recorded on the case report form (CRF) by the person designated by the investigator. A CRF is required and should be completed for each included subject. It is the investigator's responsibility to ensure the integrity of information transcribed on the CRF. CRFs must be signed by the investigator or by an authorized staff member. These signatures serve to attest that the information contained on the CRFs is true. The investigator agrees to keep records, including the identity of all participating subjects, all original signed informed consent forms, copies of all CRFs, serious adverse event forms, source documents, and detailed records of treatment disposition.

All data entered into the CRF should have source documentation available at the investigational site.

The Biostatistic Unit of ICM will enter into a database in an ongoing basis. Systems with procedures that assure the quality of every aspect of study data management will be implemented, using Clinsight® software v6.2.

The collection and management of data is carried out by the Biostatistic Unit of ICM. The conditions for data transfer of all or part of the study database are decided by the study sponsor and are the subject of a written contract.

